8.3.4 Clinical Safety Laboratory Assessments

Refer to Appendix 2 for the list of clinical laboratory tests to be performed and to the SoA for the timing and frequency.

08X3SB

The investigator or medically qualified designee (consistent with local requirements) must review the laboratory report, document this review, and record any clinically relevant changes occurring during the study in the AE section of the CRF. The laboratory reports must be filed with the source documents. Clinically significant abnormal laboratory findings are those which are not associated with the underlying disease, unless judged by the investigator to be more severe than expected for the participant's condition.

All protocol-required laboratory assessments, as defined in Appendix 2, must be conducted in accordance with the laboratory manual and the SoA.

If laboratory values from nonprotocol-specified laboratory assessments performed at the institution's local laboratory require a change in study participant management or are considered clinically significant by the investigator (eg, SAE or AE or dose modification), then the results must be recorded in the appropriate CRF (eg, SLAB).

For any laboratory tests with values considered clinically significantly abnormal during participation in the study or within 20 days after the last dose of study intervention, every attempt should be made to perform repeat assessments until the values return to normal or baseline or if a new baseline is established as determined by the investigator.

8.3.5 Neurological Exam

The full neurological exam monitors aspects of mental status, cranial nerve function, motor system function, reflexes, coordination and gait and sensory function (Appendix 12) and will be administered at screening and the post-study exam. The targeted neurological exam contains Modules 1, 2 and 5 of the general examination, focusing on arousal, cranial nerve function, and gait.

8.3.6 Mini-Mental State Examination

The MMSE-2 will be administered to the participant in paper form, scored and recorded by the principal investigator or trained designee according to the instructions in the operations manual.

8.3.7 WAIS-IV Digit Symbol Substitution Test

The DSST will be administered to the participant in paper form and scored and recorded by the principal investigator or trained designee according to the instructions in the operations manual.

8.3.8 Suicidal Ideation and Behavior Monitoring

8.3.8.1 Clinical Assessments for Suicidal Ideation and Behavior Monitoring

Suicidal ideation and behavior will be prospectively assessed during this study using the C-SSRS. The C-SSRS should be administered by trained raters at the time points indicated in the SoA. In addition, C-SSRS will be administered at any unscheduled visit where safety assessments are performed. The C-SSRS will not be routinely administered at visits with a

sole purpose of PK sampling and/or witnessed study intervention administration. Site staff should review the contents of the C-SSRS for completeness.

If the C-SSRS is administered by someone other than the investigator, consider providing the completed C-SSRS to the investigator for review, before their assessment of the participant and to further inform their evaluation.

The C-SSRS is not explicit about whether the participant specifically has ideation at the time of screening. If a participant reports a prior history of ideation/behavior at screening, the assessor should also inquire and document if this is also present at the time of the Screening Visit.

Participants who at any time during this study report suicidal ideation or behavior that is considered to be an AE, either between visits or during visit interviews, must be assessed by the investigator. Participants who report suicidal ideation with intent, with or without a plan or method (ie, a positive response to items 4 or 5 in the assessment of suicidal ideation on the C-SSRS) or suicidal behavior must be evaluated that day by a psychiatrist or other trained mental health professional who is a licensed psychologist, social worker, or mental health nurse practitioner (or comparable professional qualification in countries outside the United States). After that evaluation, only those participants whose suicidal ideation is considered by the evaluator to be passive, and who expressly deny any intent to act, and who, after evaluation, are not judged to be at serious risk for self-harm during the course of the study may continue in the study; other participants must be discontinued from study participation and receive appropriate clinical follow-up care to ensure their safety. In addition, all AEs of suicidal ideation or behavior must be recorded as an ECI (see Section 8.4.7). Sites are to designate which health care professionals are to be responsible for acute care on-site and to specify referral center(s) to be used for further evaluation.

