7 DISCONTINUATION OF STUDY INTERVENTION AND PARTICIPANT WITHDRAWAL

7.1 Discontinuation of Study Intervention

Discontinuation of study intervention does not represent withdrawal from the study. As certain data on clinical events beyond study intervention discontinuation may be important to the study, they must be collected through the participant's last scheduled follow-up, even if the participant has discontinued study intervention. Therefore, all participants who discontinue study intervention before completion of the protocol-specified treatment period will still continue to participate in the study as specified in Section 1.3 and Section 8.1.9, or a PCL (only applicable if not all procedures should be done per Section 1.3).

Participants may discontinue study intervention at any time for any reason or be discontinued from the study intervention at the discretion of the investigator should any untoward effect occur. In addition, a participant may be discontinued from study intervention by the investigator or the Sponsor if study intervention is inappropriate, the study plan is violated, or for administrative and/or other safety reasons. Specific details regarding procedures to be performed at study intervention discontinuation are provided in Section 8.1.9.

A participant must be discontinued from study intervention, but continue to be monitored in the study, for any of the following reasons:

The participant or participant's legally acceptable representative requests to discontinue study intervention.

The participant's treatment assignment has been unblinded by the investigator, MSD subsidiary, or through the emergency unblinding call center.

The participant interrupts study intervention administration for more than 1 consecutive days or has 1 cumulative missed doses.

The participant has a medical condition or personal circumstance which, in the opinion of the investigator and/or Sponsor, placed the participant at unnecessary risk from continued administration of study intervention.

The participant has a confirmed positive serum pregnancy test.

08X3SB

The participant has a positive drug screen at any time during the course of the study. The drug screen can be confirmed by a recheck at the discretion of the investigator after discussion with the Sponsor.

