7.2 Participant Withdrawal From the Study

A participant must be withdrawn from the study if the participant or participant's legally acceptable representative withdraws consent from the study.

If a participant withdraws from the study, they will no longer receive study intervention or be followed at scheduled protocol visits.

Participants may withdraw from the study at any time for any reason. If a participant withdraws from the study, they will no longer receive study intervention or be followed at scheduled protocol visits.

A participant must be withdrawn from the study if:

- The participant or participant's legally acceptable representative withdraws consent from the study.
- Participant is lost to follow-up.

Specific details regarding procedures to be performed at the time of withdrawal from the study, as well as specific details regarding withdrawal from FBR, are outlined in Section 8.1.9. The procedures to be performed should a participant repeatedly fail to return for scheduled visits and/or if the study site is unable to contact the participant are outlined in Section 7.3.

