8.4.7 Events of Clinical Interest

08X3SB

Selected serious and nonserious AEs are also known as ECIs and must be reported to the Sponsor.

Events of clinical interest for this study include:

- An overdose of Sponsor's product, as defined in Section 8.5.
- Potential DILI events defined as an elevated AST or ALT laboratory value that is greater than or equal to 3× the ULN and an elevated total bilirubin laboratory value that is greater than or equal to 2× the ULN and, at the same time, an alkaline phosphatase laboratory value that is less than 2× the ULN, as determined by way of protocol-specified laboratory testing or unscheduled laboratory testing.*

*Note: These criteria are based on available regulatory guidance documents. The purpose of the criteria is to specify a threshold of abnormal hepatic tests that may require an additional evaluation for an underlying etiology. The study-site guidance for assessment and follow-up of these criteria can be found in the Investigator Study File Binder (or equivalent). It may also be appropriate to conduct additional evaluation for an underlying etiology in the setting of abnormalities of liver blood tests including AST, ALT, bilirubin, and alkaline phosphatase that do not meet the criteria noted above. In these cases, the decision to proceed with additional evaluation will be made through consultation between the study investigators and the Sponsor Clinical Director. However, abnormalities of liver blood tests that do not meet the criteria noted above are not ECIs for this study.

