9.3 Analysis Endpoints

9.3.1 Primary Endpoints

Safety: Primary safety endpoints will include all types of adverse events and discontinuation of study intervention due to adverse event(s), in addition to laboratory safety tests, ECGs, C-SSRS and vital signs. Baseline is defined as measurements obtained pre-dose Day 1.

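### Section 8.3.8.1 ends study participation after an uncleared suicidality evaluation, against Section 7.1 and on a ground missing from Section 7.2, so scheduled C-SSRS and safety visits may stop for exactly those participants

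*Combined protocol and SAP*

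**What the plan says.** Section 8.3.8.1 requires a same-day mental health evaluation for anyone who reports suicidal ideation with intent, or suicidal behaviour. Those whose ideation is found passive, who deny intent, and who "are not judged to be at serious risk for self-harm during the course of the study may continue in the study" form the cleared group. For everyone else the rule is: "other participants must be discontinued from study participation and receive appropriate clinical follow-up care to ensure their safety".

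Section 7.1 separates stopping drug from leaving the study: "Discontinuation of study intervention does not represent withdrawal from the study". It adds that "all participants who discontinue study intervention before completion of the protocol-specified treatment period will still continue to participate in the study", and says of clinical event data that "they must be collected through the participant's last scheduled follow-up, even if the participant has discontinued study intervention". Its list of participants who must stop drug but stay monitored includes those judged to be at unnecessary risk from further dosing.

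Section 7.2 gives two grounds for mandatory withdrawal: consent is withdrawn, or the participant is lost to follow-up. On the effect of leaving it says: "If a participant withdraws from the study, they will no longer receive study intervention or be followed at scheduled protocol visits".

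Section 9.3.1 defines the primary safety endpoints as adverse events and discontinuations due to them, "in addition to laboratory safety tests, ECGs, C-SSRS and vital signs". The Schedule of Activities marks the C-SSRS and the laboratory safety tests at the Poststudy visit in both panels.

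**The concern.** The same consenting participant can be given two different statuses, and a site could defend either from the text. Under Section 8.3.8.1 the participant leaves the study. Under Section 7.1 the participant stops drug and stays.

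The participants affected are those in whom a safety event has just been observed, so any loss of scheduled data is tied to the outcome. The C-SSRS is one of the safety measures in Section 9.3.1 and, per Section 4.2.3, is included to meet regulatory guidance on prospective monitoring. The causality criteria in Appendix 3 ask whether an event resolved or improved once the drug was stopped, which needs observation after stopping. The investigator's view of relatedness also feeds the stopping rules in Section 6.6.1. Thinner observation after the event makes that judgement harder.

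**Working it through.** The question is one of consistency between sections, and the plan states no figure to reproduce.

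**1. Does Section 8.3.8.1 mean leaving the study, or only stopping drug?** It speaks of study participation and contrasts the excluded group with those who may continue in the study. Read plainly, it means leaving the study.

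**2. Does Section 7.1 reach the same participant?** Yes, if the event occurs during dosing. Its rule covers all who stop study intervention early, and its unnecessary-risk item plausibly describes this person. The result is off drug, still in the study. If the event occurs after the last dose, there is no early stop of drug, and only the mismatch with Section 7.2 remains.

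**3. Does Section 7.2 supply the exit?** No. Neither of its two mandatory grounds is suicidality. It does, however, describe what leaving the study means: no further scheduled visits.

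**4. What may stop if Section 8.3.8.1 is followed with Section 7.2?** Scheduled C-SSRS, ECG, laboratory and examination visits, and the detection of new adverse events at those visits.

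**5. What continues?**
- Section 8.1.9 covers discontinuation from the study as well as from intervention. Adverse events present at that time are followed under Section 8.4. If a poststudy visit is held early, a telephone call at the end of follow-up is called for. The poststudy visit itself is optional.
- Section 8.4.1 requires adverse event reporting from randomization to 14 days after cessation of intervention, with no exception for study exit.
- Section 8.3.8.1 makes every suicidality adverse event an event of clinical interest, and Section 8.4.3 follows such events to resolution, stabilization or another explanation, or until loss to follow-up.
- Section 8.3.8.1 also calls for the C-SSRS at any unscheduled visit with safety assessments, which depends on such a visit taking place.

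**6. Scale.** Allocation is 12 active to 4 placebo in Panel A and 9 to 3 in Panel B (Tables 4 and 5). One participant is:

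| | Active | Placebo |
|---|---|---|
| Panel A | 1/12 = 8.3% | 1/4 = 25% |
| Panel B | 1/9 = 11.1% | 1/3 = 33.3% |

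These are shares of an arm, not event rates.

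**The case against.** The strongest reply is that this is a drafting mismatch with little effect on data. Section 7.2 does not call its list exclusive, and a specific rule in Section 8.3.8.1 can be read as overriding the general one in Section 7.1. Safety reporting survives study exit. Staying in the study does not secure more data either: Section 8.10.3 leaves the procedures done after stopping drug to the investigator's discretion with sponsor agreement. All dosed participants remain in the safety population (Section 9.4.1), and Section 9.5.3 only tabulates and lists C-SSRS responses. Exclusion criterion 1 should make such events uncommon.

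Much of this stands. The amount of data lost because of Section 8.3.8.1 alone cannot be established. But no section says which rule takes precedence, and neither route guarantees a poststudy C-SSRS. Section 8.10.3 therefore strengthens the case for naming the assessments still wanted.

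Four stronger readings are tempting, and the documents do not support them:

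- **That adverse event data end at exit.** Sections 8.1.9, 8.4.1 and 8.4.3 say otherwise.
- **That Section 8.4.7 fails to list suicidality as an event of clinical interest.** The visible entries are potential drug-induced liver injury and "An overdose of Sponsor's product, as defined in Section 8.5". The amendment summary mentions study-specific events in that section, so an entry may have been redacted. Section 8.3.8.1 imposes the requirement in any case.
- **That these participants will be coded as study withdrawals.** Nothing in the text says so.
- **That a definite number of weeks of observation is lost.** The participation times are approximate, screening is given as a maximum, and the day of the Poststudy visit is not visible.

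**Conclusion.** The point holds in a limited form. Section 8.3.8.1 conflicts with Section 7.1 for events during dosing, and its ground for leaving the study is absent from Section 7.2. Followed literally, scheduled C-SSRS and visit-based safety assessments may stop for the participants who have the event, and the one visit that could still capture a closing C-SSRS is optional. Reporting of adverse events and follow-up of the suicidality event continue.

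The number affected is probably small and may be zero. In arms of 12 and 9 active participants, though, a single incompletely observed case is a visible part of the safety record. The conclusion assumes that discontinuation from study participation carries the meaning that Section 7.2 gives to leaving the study, and that no redacted text, including Section 8.10.4, which has no visible content, already resolves the status. The point should be corrected, but it does not undermine the design.

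**What to change.** 1. Reconcile Sections 8.3.8.1, 7.1 and 7.2 so that a participant not cleared at the evaluation has one defined status. This review takes no position on which clinical rule is right.
2. Whichever status is chosen, state that, unless consent is withdrawn, the poststudy C-SSRS and safety assessments already in the Schedule of Activities are still sought for these participants.
3. State that the suicidality adverse event is recorded as the reason for discontinuation, so that it counts towards the Section 9.3.1 endpoint of discontinuation due to adverse events where study intervention was stopped.

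The cost is a few sentences in an amendment. No new visit or test is needed, because the Poststudy visit and its C-SSRS are already scheduled.

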8.3.9 Photograph of Rash

Photographs of the rash are highly recommended to be taken immediately, along with any additional information that may assist the investigator to evaluate the skin reaction, skin eruption, or rash occurrence in determining etiology and study intervention relationship. See Investigator Site Binder for additional guidance.

8.4 Adverse Events, Serious Adverse Events, and Other Reportable Safety Events

The definitions of an AE or SAE, as well as the method of recording, evaluating, and assessing causality of AE and SAE and the procedures for completing and transmitting AE, SAE, and other reportable safety event reports can be found in Appendix 3.

Adverse events, SAEs, and other reportable safety events will be reported by the participant (or, when appropriate, by a caregiver, surrogate, or the participant's legally authorized representative).

The investigator and any designees are responsible for detecting, documenting, and reporting events that meet the definition of an AE or SAE as well as other reportable safety events.

Investigators need to document if an SAE was associated with a medication error, misuse, or abuse.

Investigators remain responsible for following up AEs, SAEs, and other reportable safety events for outcome according to Section 8.4.3. The investigator, who is a qualified physician, will assess events that meet the definition of an AE or SAE as well as other reportable safety events with respect to seriousness, intensity/toxicity, and causality.

8.4.1 Time Period and Frequency for Collecting AE, SAE, and Other Reportable Safety Event Information

AEs, SAEs, and other reportable safety events that occur after the participant provides documented informed consent, but before intervention randomization, must be reported by the investigator under any of the following circumstances:

if the participant is receiving placebo run-in or other run-in treatment,

if the event causes the participant to be excluded from the study,

if it is the result of a protocol-specified intervention, including, but not limited to washout or discontinuation of usual therapy, diet, placebo, or a procedure.

From the time of intervention randomization through 14 days after cessation of intervention, all AEs, SAEs, and other reportable safety events must be reported by the investigator.

Additionally, any SAE brought to the attention of an investigator any time outside the period specified in the previous paragraph also must be reported immediately to the Sponsor if the event is considered related to study intervention.

Investigators are not obligated to actively seek AEs or SAEs or other reportable safety events in former study participants. However, if the investigator learns of any SAE, including a death, at any time after a participant has been discharged from the study, and the investigator considers the event to be reasonably related to the study intervention or study participation, the investigator must promptly notify the Sponsor.

All initial and follow-up AEs, SAEs, and other reportable safety events will be recorded and reported to the Sponsor or designee within the time frames as indicated in Table 6.

Exception: A positive pregnancy test at the time of initial screening is not a reportable event unless the participant has received study intervention.

Table 6 Reporting Periods and Time Frames for Adverse Events and Other Reportable Safety Events

| Type of Event | Reporting Period: Consent to Randomization/ Allocation | Reporting Period: Randomization/ Allocation through Protocol- specified Follow- up Period | Reporting Period: After the Protocol- specified Follow- up Period | Time Frame to Report Event and Follow-up Information to Sponsor |
|---|--|---|---|---|
| NSAE | Report if: - due to protocolspecified intervention - causes exclusion - participant is receiving placeborun-in or other runin treatment | Report all | Not required | Per data entry guidelines |
| SAE | Report if: - due to protocol- specified intervention - causes exclusion - participant is receiving placebo run-in or other run- in treatment | Report all | Report if: - drug/vaccine related. (Follow ongoing to outcome) | Within 24 hours of learning of event |
| Pregnancy/Lactation Exposure | Report if: - participant has been exposed to any protocol-specified intervention (eg, procedure, washout, or run-in treatment including placebo run-in) Exception: A positive pregnancy test at the time of initial screening is not a reportable event. | Report all | Previously reported – Follow to completion/ termination; report outcome | Within 24 hours of learning of event |
| ECI (requiring regulatory reporting) | Report if: - due to intervention - causes exclusion | Report - potential DILI - requiring regulatory reporting | Not required | Within 24 hours of learning of event |
| ECI (does not require regulatory reporting) | Report if: - due to intervention - causes exclusion | Report - non-DILI ECIs and those not requiring regulatory reporting | Not required | Within 5 calendar days of learning of event |

| Type of Event | Reporting Period: Consent to Randomization/ Allocation | Reporting Period: Randomization/ Allocation through Protocol- specified Follow- up Period | Reporting Period: After the Protocol- specified Follow- up Period | Time Frame to Report Event and Follow-up Information to Sponsor | |
|---|--|---|---|---|--|
| Cancer | Report if: - due to intervention - causes exclusion | Report all | Not required | Within 5 calendar days of learning of event (unless serious) | |
| Overdose DILI=drug-induced liver injury; ECI=event of clinical interest; NSAE=nonserious adverse event; SAE=serious adverse event. | | | | | |

